8.7.3 Clinical Laboratory Evaluations

Clinical laboratory results will be converted to SI units (except albumin will use the unit of g/dL and bilirubin will use the unit of mg/dL). Change from baseline to each visit assessed and end of study will be defined using the windowing method specified in Section 6.2.2, as the visit value minus the baseline visit. Laboratory test values at each assessment and for change from baseline to each assessment will be displayed using summary statistics (number of patients, mean, median, and standard deviation). Hematology, chemistry, and coagulation results will each be summarized separately.

All clinical laboratory data will be presented in listings. Within each listing, laboratory values outside the normal ranges will be flagged as either high or low. In addition, shift tables will be presented to display the shift in the normal range categories (low, normal, high) from baseline to the final evaluation. Baseline is defined as the latest non-missing value prior to randomization.

A shift table of baseline to each assessment by CTC grade (NCI CTCAE v4.0), and a table of laboratory parameters of CTCAE Grade 3 or higher that worsened from baseline will be summarized.

A shift table comparing the baseline ALBI score to the ALBI score at each time-point will also be summarized by treatment group.

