
	
treatable progression is detected during follow-up evaluations. Any re-treatment should take place a minimum of 28 days from the last TheraSphere treatment administered to that lobe. A maximum of 2 re-treatments are permitted in any patient.

Study Visits and Follow-up	
Screening evaluations should be completed within 14 days prior to randomization. For patients randomized to sorafenib, study visits will take place every 8 weeks for as long as the patient remains on the trial. Additional visits may be scheduled as needed when initiating sorafenib treatment, and to manage any adverse events and adjustments to sorafenib dosing.
 
For Patients randomized to TheraSphere, the pre-treatment evaluations and TheraSphere treatment to the first lobe should take place during the first 3 to 4 weeks following randomization. For patients with bilobar disease, the evaluations and TheraSphere treatment to the 2nd lobe should take place during weeks 5 to 8 weeks following randomization. After TheraSphere treatment, subsequent study visits will take place every 8 weeks from randomization for as long as the patient remains on the trial.
 
After start of sorafenib therapy, patients may have additional visits as needed to adjust sorafenib dosing. Dosing of sorafenib should be consistent with the relevant label instructions, with allowance for appropriate adjustments based on the investigators medical judgment.
 
In general, follow up visits take place approximately every 8 weeks from randomization until one of the study discontinuation criteria is met (see 9.2.19). The following assessments take place at the follow-up visit:
 
 ○ ECOG Performance Status assessment ○ Standard laboratory blood draw for CBC, differential, electrolytes, BUN, glucose, liver function test, coagulation panel, and α-fetoprotein biomarker ○ Triple phase spiral abdomen CT/MRI scan ○ Spiral CT/MRI scan of chest and pelvis ○ Child-Pugh Status ○ QOL questionnaire ○ Adverse event reporting 
Patients discontinuing sorafenib treatment in either arm of the study must be followed-up for survival until consent is explicitly withdrawn or any of the other study completion criteria is met (see Section 9.2.19).

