administered (mean, 1.8; range, 1-5). Toxicities included fatigue (57%), pain (23%), and nausea/vomiting (20%); 19% exhibited grade 3/4 bilirubin toxicity. The 30-day mortality rate was 3%. Response rates were 42% and 57% based on WHO and EASL criteria, respectively. The overall median TTP was 7.9 months (95% confidence interval, 6-10.3). Median survival times differed between patients with Child-Pugh A and B disease (A, 17.2 months; B, 7.7 months; $P = .002$). Patients with Child-Pugh B disease who had portal vein thrombosis (PVT) had a median survival of 5.6 months (95% confidence interval, 4.5-6.7). Baseline age; gender; performance status; presence of portal hypertension; tumor distribution; levels of bilirubin, albumin, and alpha-fetoprotein; and WHO/EASL response rate predicted survival. These investigators concluded that patients with Child-Pugh A disease, with or without PVT, benefited most from treatment. Patients with Child-Pugh B disease who had PVT had poor outcomes. TTP and overall survival varied by patient stage at baseline.

Hilgard⁸ et al report treatment of 108 consecutive patients with advanced HCC using TheraSphere. Median overall survival from day of treatment was 16.4 months for all patients, with median time to progression of 10.0 months. Tumor response at 90 days evaluated by RECIST in 62 patients were complete or partial response 10 (16%), stable disease 46 (74%) and progressive disease 6 (10%). Toxicities were generally mild to moderate with the most common being transient fatigue during the week following administration (61%) and abdominal pain (56%). One case of radiation cholecystitis was treated with cholecystectomy. There was no Grade 3 or 4 lung toxicities. Lymphopenia was observed without clinical sequelae. Because hepatic decompensation is a known risk of yttrium-90 microsphere therapy, all elevations in bilirubin values were considered to be treatment related hepatotoxicities. For patients with normal bilirubin at enrollment, 32% experienced Grade 1 or 2 elevations and three patients developed Grade 3 elevations. For patients with elevated bilirubin at enrollment, 17% experienced Grade 2 elevations and 30% experienced Grade 3 or 4 elevations. In the majority of patients, bilirubin returned to baseline values within 4-6 weeks. The authors conclude the therapy is safe and effective, even in patients with compromised liver function.

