5.2.6 Treatment Emergent Adverse Event (TEAE)

The protocol defines a TEAE as an event that was not present at baseline or worsened in severity following the start of treatment. According to the protocol, AEs will only be collected until 30 days from discontinuation of sorafenib and after this period only AEs related to TheraSphere will be collected. However, to make the treatment groups comparable and to avoid the impact of subsequent HCC therapy on the evaluation of the AE profile, in Section 6.5.2, an AE with an onset date or a pre-existing AE worsening beyond 30 days after the end of the last study treatment initiated prior to progression date by investigator assessment, or the start date of subsequent HCC therapy, whichever comes first, will not be considered a TEAE.

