8.8 Additional Safety Analyses

A shift table comparing the baseline ECOG score to the ECOG score at each time-point will be summarized for the mITT population. This will be used to ascertain the number of patients with an ECOG score that worsens after baseline and any difference between the treatment groups.

Child-Pugh scores will be summarized for the mITT population in the same way as ECOG scores.

[REDACTED]

[REDACTED]

[REDACTED]

[REDACTED]

[REDACTED]

[REDACTED]

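### Laboratory summaries have no treatment-window cut-off, the normal-range shift uses the last value, and no baseline-to-worst shift is planned

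*SAP*

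**What the plan says.** SAP 8.7.3 plans these laboratory outputs:

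- Values and changes from baseline by visit and at end of study, using the windows of 6.2.2.
- A low/normal/high shift: "shift tables will be presented to display the shift in the normal range categories (low, normal, high) from baseline to the final evaluation".
- A CTC-grade shift from baseline to each assessment.
- A high-grade table: "a table of laboratory parameters of CTCAE Grade 3 or higher that worsened from baseline will be summarized".
- An ALBI shift by time-point.
- Full listings.

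SAP 8.8 adds that "Child-Pugh scores will be summarized for the mITT population in the same way as ECOG scores", which means at each time-point.

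None of these has an end date. In SAP 6.2.2 the end-of-study value is the latest one available. Where several values share a visit window, the one nearest the scheduled day is kept. The Week 8 window is days 2 to 85, centred on day 57.

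Adverse events are treated differently. Under SAP 5.2.6 and 6.5.2 an event is treatment-emergent only up to 30 days after the end of the last study treatment begun before investigator-assessed progression, or up to the start of subsequent HCC therapy, whichever is first. The reason given is "to make the treatment groups comparable and to avoid the impact of subsequent HCC therapy on the evaluation of the AE profile". SAP 6.4.3.11 also cuts AFP response at subsequent HCC therapy.

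**The concern.** The reason for excluding later therapy from the adverse event profile applies equally to bilirubin and transaminases. SAP 8.3.2 forms the safety groups from treatment received before progression. SAP 5.2.5 allows both study treatments as care after progression, and Appendix 4 lists Y90 for control patients, TACE and external beam radiation among later procedures. As written, a liver-test abnormality after a control patient's later Y90 would count under sorafenib alone in the laboratory tables, while the corresponding adverse event would be left out of the TEAE tables.

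The second issue is last value against worst value. For one TheraSphere cohort the protocol reports, in section 5.3: "In the majority of patients, bilirubin returned to baseline values within 4-6 weeks". A shift to the last value cannot show a rise of that kind. The one-value-per-window rule can also remove it from the by-visit tables, even when it was measured. No baseline-to-worst shift is planned to recover it, and the SAP does not say whether the Grade 3 or higher table uses windowed values or all values.

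**Working it through.** **1. Visit windows.** Scheduled days are 57, 113, 169 and 225. The midpoints are (57+113)/2 = 85, (113+169)/2 = 141 and (169+225)/2 = 197, which match SAP Table 3.

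**2. Can the Week 8 value see a short rise?** The schedule puts first TheraSphere in weeks 1-4 (taken as days 2-28) and second-lobe treatment in weeks 5-8 (days 29-56). Recovery is taken as 28 to 42 days, from Protocol 5.3. Equal weight per treatment day is my assumption.

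- First treatment: day 57 falls 57-28 = 29 to 57-2 = 55 days later. It is inside a 28-day recovery for 0 of 27 treatment days, and inside a 42-day recovery for days 15-28, which is 14/27 = 52%.
- With the permitted ±14 days, the 42-day share is 27/27 = 100% for a visit on day 43 and 0% on day 71.
- Second-lobe treatment: day 57 falls 1 to 28 days later, so it is inside the recovery period for all 28 days.

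The by-visit tables can therefore miss a short rise after first-lobe treatment, but would usually catch one after second-lobe treatment if the visit is on schedule.

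**3. Can a measured peak be dropped?** Yes. Protocol 9.1.3.2 asks for laboratory tests in weeks 5-8, and 9.2.15.1.7 asks for a draw within 48 hours of administration. These fall mostly or wholly in the Week 8 window. As an illustration, a peak on day 36 is 21 days from day 57 and a value on day 60 is 3 days from it. The day-60 value is kept.

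**4. How many final values fall after the adverse event window?** The documents give no figure, so this is a scenario calculation.

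- From Protocol 5.3: median time to progression of 5.5 months (sorafenib arm of the cited placebo-controlled trial) and 7.9 months (TheraSphere cohort).
- Assumed: median post-progression survival of 4.0 or 5.5 months, median time to death without progression of 25 months, exponential times, treatment ending at detected progression, and laboratory tests every 56 days until death.
- The window closes 30 days after detected progression. Visits are 56 days apart, so the final value is late whenever the patient reaches one more visit. Among patients with detected progression that probability is 2^(-56/(30.4375 × m)), where m is median post-progression survival in months.
- m = 4.0: 2^(-0.460) = 73%. m = 5.5: 2^(-0.335) = 79%.

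The share with detected progression comes from 200,000 simulated patients per scenario.

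| Median TTP (months) | m (months) | Progression detected | Final value late, all patients |
|---|---|---|---|
| 5.5 | 4.0 | 70% | 51% |
| 5.5 | 5.5 | 73% | 58% |
| 7.9 | 4.0 | 65% | 47% |
| 7.9 | 5.5 | 68% | 54% |

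If sampling stops two visits before the last possible one, the range is 25% to 36%. If it stops at detected progression, it is 0% in this model.

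**5. Which sampling rule holds?** The documents conflict. The protocol synopsis says that "follow up visits take place approximately every 8 weeks from randomization until one of the study discontinuation criteria is met", and 9.1.2.2 and 9.1.3.5 list laboratory tests at every 8-week visit. However, the schedules in Protocol 3.0 and SAP 6.1 split follow-up into before and after PD, defined as progression that ends further treatment. The laboratory rows carry a single follow-up mark, and AFP appears to have none after PD. The table layout available to me does not settle this.

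**The case against.** The strongest reply is that only one shift table, together with the end-of-study change, depends on the last value. The CTC-grade, ALBI and Child-Pugh shifts are by time-point, so their Week 8 and Week 16 rows are not filled with late values, and the Grade 3 or higher table may catch peaks. Significant laboratory abnormalities are also adverse events (Protocol 12.1.1). SAP 8.7.2 tabulates those inside the window, by highest grade and for events of special interest, and 6.5.2 separates events before and after the start of sorafenib. All of this stands. A reader might infer that the plan misses transient TheraSphere liver toxicity altogether, and the documents do not support that.

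A reader might also infer that the laboratory tables mainly show decline before death. That is not shown. At least 406 deaths among 520 planned patients is 78%, so most final values precede a death, but by how long is not stated, and routine sampling may stop at treatment-ending progression. Nor is it shown that a difference between arms is diluted: equal background counts shrink a ratio, not an absolute difference.

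Part of the adverse event rationale does not carry over. SAP 5.2.6 responds partly to the rule that, after 30 days off sorafenib, only TheraSphere-related events are collected. Laboratory collection has no such asymmetry, so it is mainly the subsequent-therapy half of the reason that transfers.

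Finally, where no blood was drawn, a worst-value table shows nothing. The 8-weekly sampling is a limit that the analysis cannot remove.

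What the reply leaves unanswered is the missing cut-off, the last-value rule in the normal-range shift, the absent worst-grade shift, and the unspecified input to the Grade 3 or higher table.

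**Conclusion.** The point holds as a gap in specification. The laboratory summaries lack the cut-off that the SAP adopts for adverse events, and no laboratory table is defined on the worst on-treatment value. These are descriptive tables: no test or stopping decision rests on them, and the raw values are listed. The change is worth making, but it does not threaten the trial's conclusions on efficacy.

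The size is uncertain. The share of final values after the window is about 47% to 58% of all patients if sampling runs 8-weekly to death, and near 0% if it stops at treatment-ending progression. The upper range rests on assumed survival times. It would fall if sorafenib begun before progression continues beyond it, because the window then stays open. It would rise if subsequent therapy closes the window earlier. The low figure is near zero rather than exactly zero, because exit tests (Protocol 9.1.4) and tests around TheraSphere re-treatment after progression can fall outside the window.

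**What to change.** In SAP 8.7.3:

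- Base the main laboratory toxicity tables on values inside the TEAE window of 6.5.2.
- Change the normal-range shift to the worst post-baseline value in that window, with low and high directions shown separately.
- Add a baseline-to-worst CTC-grade shift using all values in the window, including unscheduled ones.
- Apply the same window to the Grade 3 or higher table, and state that all values feed it.
- Keep the all-follow-up versions as supportive tables.
- State whether laboratory tests were collected after treatment-ending progression, reconciling the schedule with Protocol 9.1.2.2 and 9.1.3.5.

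The cost is SAP wording, reprogramming from data already collected and a few extra tables. The limit set by 8-weekly sampling remains and should be acknowledged when the tables are read.

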8.8 Additional Safety Analyses

A shift table comparing the baseline ECOG score to the ECOG score at each time-point will be summarized for the mITT population. This will be used to ascertain the number of patients with an ECOG score that worsens after baseline and any difference between the treatment groups.

Child-Pugh scores will be summarized for the mITT population in the same way as ECOG scores.

[REDACTED]

[REDACTED]

[REDACTED]

[REDACTED]

[REDACTED]

[REDACTED]

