6.2.2 Windows

For the purpose of statistical analysis, time windows will need defining for presentations that summarize values by visit. The windows for the visits following baseline will be constructed in such a way that the upper limit of the interval falls half way between the two visits (the lower limit of the first post-baseline visit will be Day 2), as shown below. The assignment of data to visit windows will use the relative day defined in Section 6.2.1.1.

Table 3 Analysis Windows for Assessments Performed at Eight Week Intervals

Week	Scheduled Day	Visit Window for Analysis (Days)
Week 8	57	2 – 85
Week 16	113	86 – 141
Week 24	169	142 – 197
...		
End of Study		Latest assessment available*

*Last assessment should be assigned to a Week X based on the visit windows as well as to the end of study evaluation.

If a patient has more than 1 assessment occurring in the same visit window, the data from the assessment closest to the scheduled day will be used. If 2 assessments have the same distance from the scheduled day, the data of the assessment after the scheduled day will be used. Note that the visit windows will not be used for time-to-event endpoints and subject-level tumor response endpoints (i.e. objective response rate and disease control rate).

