6.4.2.5 Time to Symptomatic Progression

Time to symptomatic progression (TTSP) is defined as the time from date of randomization to date of assessment of ECOG performance status >1 with or without tumor progression based on investigator assessment according to RECIST criteria v1.1. The symptomatic progression is confirmed at the first two subsequent evaluations at least 8 and 16 weeks later, respectively. The date of the first ECOG performance status >1 will be used as the event date in the TTSP analysis (assuming ECOG performance status >1 at the first two subsequent evaluations at least 8 and 16 weeks later, respectively). Illustrative examples are provided in Table 7.

Table 7 Examples of Symptomatic Progression

Week X	Week X+8	Week X+16	Week X+24	Week X+32	TTSP Event
ECOG>1	ECOG>1	ECOG>1	ECOG≤1	ECOG≤1	Yes, event at Week X

ECOG>1	ECOG>1	Missing	ECOG>1	ECOG≤1	Yes, event at Week X
ECOG>1	Missing	ECOG>1	ECOG>1	Missing	Yes, event at Week X
ECOG>1	ECOG≤1	ECOG>1	ECOG>1	Missing	No
ECOG>1	No further ECOG assessments				No
ECOG>1	ECOG>1	No further ECOG assessments			No

Week X denotes that week of the first occurrence of ECOG >1

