8.6.2.3 Time to Symptomatic Progression (TTSP)

TTSP rates will be derived from the Kaplan-Meier estimates for each treatment group; 3, 6, 9, and 12 month TTSP rates will be presented, together with 95% CIs. Quartiles will be presented and 95% CIs will be calculated on the quartiles for each treatment group. A log-rank (two-sided) test will be used to compare TTSP between the two treatment groups at a 0.05 significance level. The HR and corresponding 95% CI will be computed from a Cox proportional hazards model. Plots of the Kaplan-Meier curves will be provided for each treatment group. This analysis will be performed on both the mITT and PP populations.

TTSP (Months) = (Date of first ECOG >1/censor – Date of Randomization + 1)/ 30.4375.

The censoring is performed as follows:

- 1) If a patient does not have a post baseline ECOG assessment, then the TTSP will be censored at the randomization date, regardless of whether or not symptomatic progression has been observed.
- 2) If a patient received a subsequent HCC therapy before symptomatic progression or in the absence of symptomatic progression (note that for this scenario a subsequent HCC therapy may occur before the assessment of ECOG>1 or before either confirmation of ECOG>1 at the first two subsequent assessments at least 8 and 16 weeks later, respectively), the TTSP time will be censored at the last valid post baseline ECOG assessment on or before the start date of the subsequent HCC therapy. If the patient has no post-baseline ECOG assessments on or before the start date of the subsequent HCC therapy, the patient will be censored at the randomization date.
- 3) If a patient did not have a symptomatic progression and did not receive subsequent HCC therapy, the TTSP time will be censored at the last post baseline ECOG assessment date or at the randomization date if the patient does not have any post-baseline ECOG assessments.
- 4) If a patient had symptomatic progression immediately after two or more missed visits (note that for this scenario two or more missed visits may occur before the assessment of ECOG>1 or before either confirmation of ECOG>1 at the first two subsequent assessments at least 8 and 16 weeks later), the patient will be censored at the last post baseline ECOG assessment before the missed visits. If the patient has no post-baseline ECOG assessments before the missed visits, the patient will be censored at the randomization date.

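### The per-visit ECOG and Child-Pugh shift tables in SAP 8.8 cannot give the number of patients who worsen, which is the purpose stated for them

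*SAP*

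**What the plan says.** SAP 8.8 describes the ECOG table: "A shift table comparing the baseline ECOG score to the ECOG score at each time-point will be summarized for the mITT population". The next sentence gives its purpose: "This will be used to ascertain the number of patients with an ECOG score that worsens after baseline and any difference between the treatment groups". A further sentence ties Child-Pugh to it: "Child-Pugh scores will be summarized for the mITT population in the same way as ECOG scores". ALBI has a similar table in SAP 8.7.3: "A shift table comparing the baseline ALBI score to the ALBI score at each time-point will also be summarized by treatment group". ALBI carries no statement about counting patients who worsen, and SAP 8.7 places it under the Safety Population, not the mITT.

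SAP 7.3 leaves missing data to the relevant parts of Section 8. No rule for these three scores is visible in 8.7.3 or 8.8. SAP 6.2.2 defines an End of Study value, the latest assessment available, and notes: "Last assessment should be assigned to a Week X based on the visit windows as well as to the end of study evaluation". Section 8.8 does not say whether that row appears in its tables. Redacted text follows the Child-Pugh sentence in 8.8.

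**The concern.** The purpose is a count of patients, compared between arms. The table is a series of cross-sections. A patient who is worse at two visits is counted twice, one who recovers is counted and then not, and one who dies leaves the later tables without any visible record there. A reader who wants the number who worsened must add overlapping counts or pick a visit.

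The denominators matter too. Unless the table shells add a category, each visit covers only patients who are alive and have a score. Protocol 9.1.2.2 and 9.1.3.5 allow telephone contact alone for patients who stop treatment on progression and cannot attend, so scores can cease before death.

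Hepatic decompensation is among the serious events that SAP Section 2 lists as possibly associated with TheraSphere, so a clear count of patients whose Child-Pugh worsened, by arm, is worth having.

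**Working it through.** **1. Can the table give the count?** Take three invented patients, all ECOG 1 at baseline.

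| Patient | Week 8 | Week 16 | Week 24 |
|---|---|---|---|
| A | 2 | died | – |
| B | 2 | 2 | 1 |
| C | 1 | 1 | 2 |
| Worse / assessed | 2/3 | 1/2 | 1/2 |

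All three worsened. The visit counts add to 2 + 1 + 1 = 4, and the largest single visit gives 2. The End of Study row gives 2 (A and C), because B had recovered. Only the worst post-baseline value gives 3. Worsening that arises between a patient's last visit and death is in none of these.

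**2. Do other visible analyses supply it?**
- TTSP (SAP 6.4.2.5) counts ECOG above 1 only with confirmation: "The symptomatic progression is confirmed at the first two subsequent evaluations at least 8 and 16 weeks later, respectively". Without confirmation, and with no subsequent HCC therapy, "the TTSP time will be censored at the last post baseline ECOG assessment date" applies (SAP 8.6.2.3). A patient first above 1 at Week 8 who dies at Week 20 is not an event.
- TTUP (SAP 6.4.2.4) has Child-Pugh above B7 as one of seven listed conditions, captured through one investigator yes/no item. It does not isolate liver function.
- Overall survival counts every death, but not what preceded it.
- Fatal, serious and grade 3 or higher TEAEs (SAP 8.7.2) count patients. The TEAE window closes 30 days after the last study treatment begun before progression, or at subsequent HCC therapy if earlier (SAP 6.5.2).
- The table of worsened grade 3 or higher laboratory parameters (SAP 8.7.3) covers single analytes, not the composite scores.

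**3. How far do the denominators shrink?** Inputs: medians of 10.7 and 14.2 months (SAP 4.4); effective sample size 468, 1:1, so 234 per arm (SAP Appendix 5 and 4.2). As a check on these inputs, 10.7/14.2 = 0.7535, matching the stated 0.754. A group sequential calculation with rho = 1.5 and looks at 188, 250 and 417 deaths returns two-sided boundaries of 0.0151, 0.0151 and 0.0363 and power of 0.798, so the plan's figures reproduce.

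Assuming exponential survival, S = 0.5^(m/median), with m = 7 × weeks / 30.4375.

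| Visit | m (months) | Dead, control | Dead, TheraSphere | Alive of 234, control | Alive of 234, TheraSphere |
|---|---|---|---|---|---|
| Week 8 | 1.84 | 11.2% | 8.6% | 208 | 214 |
| Week 24 | 5.52 | 30.1% | 23.6% | 164 | 179 |
| Week 48 | 11.04 | 51.1% | 41.7% | 114 | 137 |

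Missed visits reduce these numbers further.

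**4. Can survivor tables mislead?** Two illness-death illustrations follow. All rates are assumed; none is in the documents.
- *Equal worsening, unequal death afterwards.* Both arms worsen at 0.08/month and die at 0.03/month before worsening; median survival after worsening is 6 versus 1.5 months. By Week 48, 51.2% of each arm have worsened, but the Week 48 table shows 46.3% versus 18.1%. The share ever seen worse at an 8-weekly visit is 45.9% versus 34.0%.
- *Unequal worsening.* Control worsens at 0.06/month, the other arm at 0.12/month. Death is 0.04/month, multiplied by 4 (control) or 8 (other arm) after worsening. By Week 48, 62% versus 40% have worsened, but the table shows 38% versus 33%. The share ever seen worse at a visit is 46% versus 35%. With a multiplier of 4 in both arms, the table gap at Week 48 is 24 points against 22 for ever worsened, so nothing is masked.

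**The case against.** The strongest reply is that these are descriptive tables and the trial looks at the same harm in several other places. That largely stands. A reader might infer that ECOG and Child-Pugh are analysed only here, or that decompensation followed by death vanishes from the comparison of arms. The documents do not support either reading: TTSP and TTUP use these scores, and deaths and liver events enter overall survival and the adverse event and laboratory tables.

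A second reply is the End of Study row. If it is applied in 8.8, a patient who worsens at Week 8 and dies before Week 16 is counted there. That also stands, but the row recovers only worsening still present at the last visit.

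Third, the SAP says the tables are for the mITT population and does not rule out a missing category, so a survivor-only denominator is inferred from the absence of a rule. The redacted text in 8.8 may also bear on this.

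Fourth, a reader might infer from the second illustration that the tables would hide a serious harm. It does not show that. The masking depends on the assumed 8-versus-4 contrast and is strongest late. In the same model the tables show 16% versus 9% at Week 8 and 31% versus 22% at Week 24. The harmful arm would also have a median survival of 6.9 months against 10.8, which the primary endpoint would show.

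Finally, a worst value is not neutral. It rises with the number of assessments, and so with survival, and it may include values after subsequent HCC therapy.

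**Conclusion.** The mismatch between purpose and table is real for ECOG and Child-Pugh. As visible, SAP 8.8 promises the number of patients who worsen and any difference between arms, and specifies a table from which that number cannot be read. ALBI shares the layout but not the stated purpose.

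The loss of patients to death, about 30% and 24% by Week 24 and 51% and 42% by Week 48, rests on the design medians and exponential survival. The illness-death figures show only that later-visit percentages can differ from cumulative worsening in either direction. They are not estimates for this trial.

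The consequence is limited to these descriptive safety tables. It does not extend to the whole safety comparison, and it leaves the sample size, alpha and the overall survival test unchanged.

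**What to change.** In SAP 8.8, for ECOG and Child-Pugh in the mITT population:
- Add a baseline-to-worst-post-baseline shift table by randomized arm, with a row for patients with no post-baseline assessment. Take the number who worsen from this table.
- Add died and not-assessed rows to each time-point table, so that every column sums to the arm's mITT total.
- State whether the End of Study row of 6.2.2 appears.
- Show the number of assessments per arm beside the worst-value table, and repeat that table using only values before subsequent HCC therapy.

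In SAP 8.7.3, use the same layout for ALBI in that section's own population, as a consistency improvement.

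The cost is SAP wording and a few extra tables from scores and death dates already collected. The worst-value table still misses decline between the last visit and death, so it should be read together with the died rows.
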